8.3.8 REPORTING OF PREGNANCY

We will inform the consenting parents of minor participants at the beginning of the process that we will respect the confidentiality of our teenage participants. It is important for us to let teenage participants know that they can be honest about sensitive topics without fear of reprisal from their parents. However, participants will also be informed about limits to confidentiality. If we learn that a subject has potential to harm him or herself, or another individual, we will break confidentiality and take steps to prevent harm. Similarly, any evidence of potential child abuse will be reported to Child Protective Services.

8.3.9 DEFINITION OF UNANTICIPATED PROBLEMS

This protocol uses the definition of Unanticipated Problems as defined by the Office for Human Research Protections (OHRP). OHRP considers unanticipated problems involving risks to participants or others to include, in general, any incident, experience, or outcome that meets all of the following criteria:

- Unexpected in terms of nature, severity, or frequency given (a) the research procedures that are described in the protocol-related documents, such as the Institutional Review Board (IRB)-approved research protocol and informed consent document; and (b) the characteristics of the participant population being studied;
- Related or possibly related to participation in the research (“possibly related” means there is a reasonable possibility that the incident, experience, or outcome may have been caused by the procedures involved in the research); and
- Suggests that the research places participants or others at a greater risk of harm (including physical, psychological, economic, or social harm) than was previously known or recognized.

8.3.10 UNANTICIPATED PROBLEMS REPORTING

The investigator will report unanticipated problems (Ups) to the reviewing Institutional Review Board (IRB). The UP report will include the following information:

- Protocol identifying information: protocol title and number, PI's name, and the IRB project number
- A detailed description of the event, incident, experience, or outcome
- An explanation of the basis for determining that the event, incident, experience, or outcome represents an UP
- A description of any changes to the protocol or other corrective actions that have been taken or are proposed in response to the UP

To satisfy the requirement for prompt reporting, Ups will be reported using the following timeline:

- Ups that are serious adverse events (SAEs) will be reported to the IRB and to the study sponsor/funding agency within 10 days of the investigator becoming aware of the event
- Any other UP will be reported to the IRB and to study sponsor/funding agency within 30 days of the investigator becoming aware of the problem
- All Ups should be reported to appropriate institutional officials (as required by an institution's written reporting procedures), the supporting agency head (or designee), and the Office for Human Research Protections (OHRP) within 30 days of the IRB's receipt of the report of the problem from the investigator

9 STATISTICAL CONSIDERATIONS

9.1 STATISTICAL HYPOTHESES

- Primary Endpoint(s): Change in Brain activation and connectivity in the task-control network (TCN)

We hypothesize that **(a)** both groups will have increased activation and functional connectivity in task-control network after therapy vs. before therapy; however, **(b)** the increase will be greater in CBT+CCT vs. CBT only group. Baseline and week 12 assessment will evaluate pre- to post-CBT changes in brain activation and function connectivity in the task-control network including fronto-parietal and cingulo-opercular regions mediating cognitive control. Functional activation and connectivity of these brain regions are assessed using a conflict interference computer task performed during MRI scanning.

- Secondary Endpoint(s):
 - (1) Change in behavioral performance on the conflict interference task and tasks testing cognitive control capacity included in the NIH Toolbox: We hypothesize that **(a)** both groups will have improved behavioral performance on the conflict interference task and tasks testing cognitive control capacity included in the NIH Toolbox; however, **(b)** these effects will be greater in CBT+CCT vs. CBT group. This will be evaluated using two measures of the same construct at baseline and week 12. Pre- to post-CBT changes in the behavioral performance in a conflict interference task will be collected, as well as composite score from tasks included in the NIH toolbox.
 - (2) Change in Pediatric Anxiety Rating Score (PARS): We hypothesize that relative to CBT group, anxiety severity will be reduced more and treatment response rate will be higher in CBT+CCT group. This will be evaluated at baseline and week 12 through the PARS, a 50 question interview-based tool used to assess for the presence and severity of anxiety symptoms in children and adolescents utilizing parental and youth input to guide clinician ratings. The total scores on this scale range from 0 to 30, with scores above 13 indicating clinically meaningful anxiety.

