4 STUDY DESIGN

4.1 OVERALL DESIGN

We hypothesized that computerized cognitive training (CCT), through engaging the task-control network and increasing cognitive control capacity, may augment the CBT response. In this study, eighteen clinically anxious children ages 7 to 17 will be recruited and assigned to CBT+CCT for up to 12 weeks; thirty-six age- and gender-matched anxious children will be recruited and assigned to CBT only for up to 12 weeks. Before and after therapy, all participants may complete structured clinical assessment of anxiety, a computerized evaluation of cognitive control capacity (e.g., NIH Toolbox; Zelazo, Anderson, Richler, Wallner-Allen, and Beaumont, 2013) and MRI scanning during a cognitive interference task and resting-state to assess brain activation and functional connectivity in the TCN. However, at P.I. discretion, participants may not be required to complete an fMRI. Participants may also complete structured clinical assessment of anxiety, computerized evaluation of cognitive control capacity, and MRI scanning during therapy.

This study will be incorporated into an ongoing fMRI study (HUM00118950, PI [name]) investigating dimensional brain-behavioral predictors of CBT outcomes in pediatric anxiety. In the parent R01 (HUM00118950), 210 youths (7-17 years) with impairing anxiety are being recruited and randomized 2:1 to receive 12-week CBT or a non-active control therapy, “relaxation and mentorship therapy” (RMT);

multilevel data including fMRI, DTI and clinical measures are collected before and after treatment. As part of the parent study, RMT completers are offered study CBT (at no cost), without additional scanning.

Study activities that may be completed remotely (i.e., Millisecond behavioral assessment, clinical measures and assessments, CCT, and CBT through the parent study) will be conducted via an encrypted HIPAA-compliant video conferencing platform (e.g., BlueJeans, Zoom), phone call, and/or Millisecond/Qualtrics links. It will be standard practice to conduct as many procedures remotely as possible to better protect subject(s)/parent(s) and staff against the risk of COVID-19. However, when remote visits are not possible (e.g., NIH toolbox behavioral assessments, fMRI), in-person visits will be allowed and the study will follow all U-M safety guidelines for entering and being in U-M buildings (e.g., COVID screenings, PPE, social distancing, etc.).

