Eighteen RMT subjects in the parent study will be recruited to our CBT+CCT group, and thirty-six age- and gender-matched CBT subjects in the parent study will be recruited to our CBT control group. The proposed study may add:

- 1) For all fifty-four subjects recruited from parent study:
 - a. NIH Toolbox and/or Millisecond behavioral assessment before and after the CBT course of therapy as well as once before the RMT course of treatment and once at about 3 weeks of CBT and another time if completing the fMRI following 4 weeks of at home CCT for the CBT+CCT group
 - b. BRIEF2 questionnaire before, after, and at about week 3 of the CBT course of treatment, as well as once before the RMT course of treatment and at the fMRI following 4 weeks of at home CCT for the CBT+CCT group
 - c. Clinical assessment of anxiety at week 3 of CBT treatment.
- 2) For patients originally randomized to RMT in the parent study who wish to enroll in the current study during their Optional CBT participation:
 - a. augmentation of the CBT offered by the parent R01 study with CCT games delivered prior to each CBT session (CBT+CCT) along with a brief survey (the Self-Assessment Manikin) they may be asked to complete before and after CCT
 - b. fMRI following 4 weeks of at home CCT, and fMRI following CBT+CCT completion
 - c. Clinical measures and assessments before and throughout the course of CBT treatment
 - d. at home CCT (~30 min/day), 5x per week, for up to 4 weeks, for up to two weeks before starting CBT and for up to 4 weeks after starting CBT, along with a brief survey (the Self-Assessment Manikin) they may complete before and after CCT

Data analyses will compare pre- and post-CBT data from the parent study with pre- and post-CBT+CCT data collected for the proposed study. These data will include NIH Toolbox and/or Millisecond measures of behavioral capacity for cognitive control; multi-modal assessment of TCN with fMRI, resting state and DTI; and, detailed assessment of anxiety symptoms using both clinician-interview and self-report. Pre- to post-therapy change in anxiety severity (clinician-measured) will serve as the primary outcome variable; regression analyses will be used to test for associations of anxiety change with changes in brain-behavioral indices of cognitive control following CBT compared to CBT+CCT. To increase clinical relevance of study results, analyses will also consider responder status, a common end point for clinical trials.

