8.1.3 FMRI SCANS

Staff and subjects/parents will follow the fMRI Lab COVID-19 safety guidelines at all times.

Overview: fMRI scans will be performed at two time points for the parent protocol – after the initial assessment and prior to the onset of the first course of treatment (~0 - 14 days prior for anxious participants), and after the completion of treatment (~0 - 30 days after the last therapy session. For the current protocol, an additional scan may be performed following completion of the 4 weeks of at home CCT and at the end of CBT+CCT. If more than about 6 weeks have elapsed since their second scan through the parent protocol, a repeat scan may be obtained prior to the onset of CBT+CCT. Immediately prior to the fMRI session, we will review the MRI protocol, repeat screening for contra-indications to MRI and have subjects remove all objects from their person that could be disturbed by the magnetic fields. They will then undergo the fMRI session (approximately 1-1.5 hours for setup and acquisition). The fMRI methods described below will be the same for each of the scans participants will undergo. Should a participant wish to receive an image of their brain, one will be provided. Please note that, at P.I. discretion, participants may not be required to complete an fMRI.

Assessments prior to each fMRI scan:

- 1) Review of fMRI safety form (copy to fMRI lab)
- 2) Urine pregnancy test for women who endorse possibility of pregnancy.

Placement in the Scanner:

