9.3.2 ANALYSIS OF THE PRIMARY ENDPOINT(S)

We hypothesize that CCT will further increase TCN activation and connectivity. The hypothesis will be tested using 2 (within-subject: pre vs. post) x 2 (between-subject: CBT vs. CBT+CCT) repeated-measures ANOVAs on brain activation and connectivity in TCN.

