9.3.3 ANALYSIS OF THE SECONDARY ENDPOINT(S)

- (1) We hypothesize that CCT will increase cognitive control capacity (measured by NIH toolbox CC composite scores and behavioral performance on the MSIT task and/or Millisecond scores). The hypothesis will be tested using 2 (within-subject: pre vs. post) x 2 (between-subject: CBT vs. CBT+CCT) repeated-measures ANOVAs on behavioral performance.
- (2) Repeated-measure ANOVAs will be conducted to examine effect of CCT on CBT. We hypothesize that anxiety severity (i.e., continuous PARS score) will be reduced more in CBT+CCT group, relative to CBT group. Chi-square tests will be used to test for differences in the ratio of CBT responders: non-responders between CBT+CCT and CBT group. We hypothesize that CBT+CCT will have more responders than the CBT.

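### Hypothesis (a), a rise after therapy in both groups, has no comparator: both ANOVA groups receive CBT, and the change over RMT enters no analysis in Section 9

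*Combined protocol and SAP*

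**What the plan says.** Section 9.1 splits the hypotheses for the primary and first secondary endpoints into two parts. Part (a) for the task-control network (TCN) is that "both groups will have increased activation and functional connectivity in task-control network after therapy vs. before therapy". Part (a) for cognitive control is that "both groups will have improved behavioral performance on the conflict interference task and tasks testing cognitive control capacity included in the NIH Toolbox". Part (b) of each is that the gain is larger with CBT+CCT. Section 4.2 states the same pair under aims 1 and 2.

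The planned models are "2 (within-subject: pre vs. post) x 2 (between-subject: CBT vs. CBT+CCT) repeated-measures ANOVAs on brain activation and connectivity in TCN" (Section 9.3.2) and "2 (within-subject: pre vs. post) x 2 (between-subject: CBT vs. CBT+CCT) repeated-measures ANOVAs on behavioral performance" (Section 9.3.3(1)). Both sections introduce the model as a test of what CCT adds. Neither names a test for part (a).

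Section 4.1 sets the scope: "Data analyses will compare pre- and post-CBT data from the parent study with pre- and post-CBT+CCT data collected for the proposed study". It also describes the parent study, which randomises 2:1 to 12 weeks of CBT or to RMT, a non-active control, and in which "multilevel data including fMRI, DTI and clinical measures are collected before and after treatment". Section 8.1.3 says that "fMRI scans will be performed at two time points for the parent protocol", placed before and after the first course of treatment, with the same scan methods each time. The interference task (MSIT) is one of the tasks that may be run at each scan. For youth who move from RMT to CBT+CCT, Section 4.1 allows Toolbox and/or Millisecond testing before RMT and again before CBT.

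**The concern.** Part (a) is worded as a change after therapy, for youth aged 7 to 17 who repeat the same scanner task and cognitive tests some months apart. Performance and activation may shift through retesting or maturation alone. In a model where every participant receives CBT, any such shift lands in the time effect and cannot be told apart from a therapy effect.

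The risk is one of attribution: a significant time effect could be read as CBT engaging the TCN or improving cognitive control when the same change might occur under RMT. Section 9.2 says the pilot is meant to supply effect sizes for a later application. A pre-post effect that contains drift would be a poor input to that.

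A comparator exists by design. The parent's RMT arm is randomised, non-active, and scanned at the same two points with the same methods.

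**Working it through.** **Inputs.** Section 5: 36 CBT and 18 CBT+CCT planned; retention 96.2%; usable-motion rate 89%; expected usable 32 and 14. Section 9.3.1: two-tailed 0.05 in general; for fMRI, 0.005 uncorrected or 0.05 corrected. Section 9.2 states that no pilot data support a power analysis, so no SD or drift is given. Drift is therefore assumed, in units of the SD of change.

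**The plan's own figure.** 36 × 0.962 × 0.89 = 30.8 (stated 32) and 18 × 0.962 × 0.89 = 15.4 (stated 14). The total is 46.2 against 46. Each arm agrees within two participants, so 32 and 14 are used below.

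**Chance of declaring an increase when therapy does nothing.** For a paired test with n youth and drift d, the noncentrality is d × √n. With n = 32 this is 0.3 × √32 = 1.70 and 0.5 × √32 = 2.83. The upper-tail probability beyond the two-sided critical value, from the noncentral t on n − 1 degrees of freedom, is:

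| Threshold | Drift d | CBT, n = 32 | CBT+CCT, n = 14 | Pooled, n = 46 |
|---|---|---|---|---|
| 0.05 | 0 | 2.5% | 2.5% | 2.5% |
| 0.05 | 0.2 | 19.4% | 10.3% | 26.4% |
| 0.05 | 0.3 | 37.6% | 17.9% | 51.2% |
| 0.05 | 0.5 | 78.2% | 41.0% | 91.3% |
| 0.005 | 0.3 | 11.2% | 3.3% | 19.5% |
| 0.005 | 0.5 | 43.8% | 11.4% | 66.8% |

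The pooled column approximates the ANOVA time effect as one paired test in all 46. If an increase had to be significant separately in both groups, the chance is the product of the two group columns. At 0.05 that is 0.376 × 0.179 = 6.7% (d = 0.3) and 0.782 × 0.410 = 32.1% (d = 0.5), against a nominal 0.025 × 0.025 = 0.06%.

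**With RMT as comparator.** If drift is the same over CBT and over RMT it cancels in the difference, and the upper-tail error returns to 2.5%. The detectable difference at 80% power, by the normal formula with 32 CBT youth and an assumed 14 RMT youth with usable scans before and after RMT, is (1.96 + 0.84) × √(1/32 + 1/14) = 2.80 × 0.320 = 0.90 SD of change. The noncentral t gives 0.92, or 0.88 with 16 RMT youth. The uncontrolled paired test at n = 32 detects 0.51, but it answers a different question.

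**The case against.** **The plan never says it tests (a) with the time effect.** This is right. Section 9.3 ties the ANOVA to the effect of CCT, and part (a) is worded as a change in time, not as a causal claim. The time effect is the implied test because nothing else in Section 9 could address (a). As a pooled effect it would not even show an increase in each group.

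**CBT versus RMT belongs to the parent study.** The parent's analysis plan is not in these documents, and leaving the contrast there is a defensible scope choice. What can be said is that this plan's Section 9 does not use it. If (a) is to be a hypothesis here, it needs either the comparator or a descriptive label.

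**The control data may be thin.** Section 4.1 lists the pre-RMT cognitive tests among things the study may add, and scans can be waived at investigator discretion. This protocol's groups are RMT youth who opt in and matched CBT youth, not the full randomised arms. All of this stands and limits the contrast, most of all for Toolbox and Millisecond.

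**The percentages depend on the threshold and on assumed drift.** They do. At the uncorrected fMRI threshold the range for 32 youth is 11% to 44%. The upward direction is also assumed; a downward drift would hide a real rise.

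A reader might be tempted by three stronger readings.

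- That the RMT-period scans go wholly unused. Sections 5.5 and 8.1.3 let the post-RMT scan serve as the CBT+CCT baseline; it is the pre-RMT scan and the change over RMT that are absent.
- That each CBT+CCT youth's own RMT change is a good control. RMT change runs from first to second scan and CBT+CCT change from second to third or later, so practice need not cancel. The post-RMT scan may also enter both changes with opposite sign.
- That the exploratory aim linking TCN change to anxiety change rests on (a). Those regressions compare individuals, and a uniform shift moves the intercept, not the slope.

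**Conclusion.** The point holds for hypothesis (a) only. As planned, a rise in TCN function or cognitive control within either group cannot be attributed to therapy, and the change over RMT that could help separate the two enters no analysis in Section 9.

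Under an assumed upward drift of 0.3 to 0.5 SD of change and no therapy effect, a paired test in 32 CBT youth would declare an increase in about 38% to 78% of trials at two-sided 0.05 and 11% to 44% at 0.005. These figures illustrate the risk; they do not estimate drift in this trial.

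It would be wrong to infer from this that the CBT+CCT versus CBT comparison lacks a control. Hypothesis (b) has its own comparator and is not judged here. The change is worth making before analysis, because it limits what may be claimed and uses a less biased contrast at little cost.

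**What to change.** 1. In Section 9.3.2, add the contrast of CBT pre-post change minus RMT pre-post change. Both should be first-course and from first to second scan. Report it as an estimate with a confidence interval.
2. In Section 9.3.3(1), do the same for MSIT performance, and for Toolbox/Millisecond where tests both before and after RMT exist. State that these tests are optional, and that this protocol's groups are not the full randomised arms.
3. Report the bare pre-post change within each group, CBT+CCT included, as descriptive, and do not attribute it to therapy.
4. Do not use the within-person difference between CBT+CCT change and RMT change as a test of (a).

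The cost is SAP wording and one added contrast per outcome; no new visits are needed. The interval will be wider than for the bare pre-post change, with a detectable difference of about 0.9 SD of change at 32 versus 14. The result should be read as an estimate and not as a powered test.

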9.2 SAMPLE SIZE DETERMINATION

No pilot data is currently available to enable a power analysis, but the proposed study will generate effect sizes for an R01 or R61/R33 application that will build from this pilot study.

9.3 STATISTICAL ANALYSES

9.3.1 GENERAL APPROACH

Data will be analyzed using statistics software such as MATLAB, SPSS and R software. For descriptive statistics, means with standard deviation and range will be computed for continuous data (all brain and behavioral data and some of the clinical data). In general, statistical significance is reported based on $p < 0.05$ two-tailed; for the fMRI data, $p < 0.005$ uncorrected or $p < 0.05$ corrected for family-wise error or false discovery rate where applicable.

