Cognitive control is the ability to direct attention and cognitive resources to regulate behavior and emotion. Behavioral and neuropsychological data have consistently shown increased anxiety symptoms associated with lower levels of cognitive control in children and adolescents (Han, Helm, Iucha, Zahn-Waxler, Hastings, and Klimes-Dougan, 2016; Hopkins, Lavigne, Gouze, LeBailly, and Bryant, 2013; Muris, van der Pennen, Sigmond, and Mayer, 2008). At the neural level, cognitive control can be measured by functional magnetic resonance imaging (fMRI) in a network encompassing superior parietal, dorsal lateral (dlPFC) and medial (mPFC) prefrontal cortex (Menon, 2011). This network is called the task-control network (TCN), activated during a variety of cognitive tasks. In adults, increased anxiety has been associated with reduced dlPFC activation in cognitive tasks with or without threat stimuli in community samples (Bishop, Duncan, Brett, and Lawrence, 2004; Bishop, 2009), interpreted as impoverished recruitment of TCN in regulating attention for high-anxious individuals, even when threat is absent. Our own study of pediatric anxiety disorders, showed dlPFC hypoactivation in error processing during a cognitive interference task in pediatric anxiety, suggesting insufficient engagement of TCN may contribute to a deficient capacity for adjusting repetitive anxious thoughts and behavior during an error ([name] et al., 2013). Given these findings, increasing TCN functions may help to reduce the anxiety symptoms.

2.2.3 NEURALLY TARGETED COGNITIVE TRAINING TO INCREASE COGNITIVE CONTROL MAY AUGMENT TREATMENT OUTCOME IN PEDIATRIC ANXIETY.

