“3” ring finger. Interference occurs when the target number position is incongruent with its ordinal value (e.g., “3” presented at the 1st position) and with different, flanking numbers (e.g., “11”). In the control condition, the target number is always presented in a position compatible with its ordinal value (e.g., “1” presented in the first position) and flanked by zeroes (e.g., “100”). Our event-related version of the MSIT allows for separation of fMRI BOLD signal associated with correct incongruent, correct congruent and error trials. We have extensive experience with this task, as demonstrated by our preliminary data, and have shown that it reliably activates the dACC, as well as vLPFC in children and adolescents with and without anxiety symptoms. MSIT data collection occurs over approximately 15 minutes.

Post-scan debriefing: Subjects may answer several questions about how much they were frustrated/flustered with the task. Subject will also be asked to complete a Medication Adherence.

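### Section 9.3.1 lets the primary imaging result be declared significant without correction, and no section fixes the mask, contrast or number of tests, so error control rests on a choice the plan does not make

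*Combined protocol and SAP*

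**What the plan says.** **Threshold.** Section 9.3.1 uses two-tailed 0.05 in general and makes a special rule for imaging: "for the fMRI data, $p < 0.005$ uncorrected or $p < 0.05$ corrected for family-wise error or false discovery rate where applicable". No other section says which branch governs the primary test, or chooses between family-wise error (FWE) and false discovery rate (FDR).

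**Primary test.** Section 9.1 makes change in TCN activation and connectivity primary. Section 9.3.2 fixes the model as two-by-two (time by group) "repeated-measures ANOVAs on brain activation and connectivity in TCN". The plural is not counted.

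**Regions.** Section 2.2.2 describes "a network encompassing superior parietal, dorsal lateral (dlPFC) and medial (mPFC) prefrontal cortex". Section 9.1 instead names fronto-parietal and cingulo-opercular areas, in an open-ended list. Neither is a mask or a list of regions.

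**Contrast.** Section 8.1.3 says the interference task (MSIT) "allows for separation of fMRI BOLD signal associated with correct incongruent, correct congruent and error trials". No contrast is named for the primary test. The sponsor's motivating study in Section 2.2.2 "showed dlPFC hypoactivation in error processing during a cognitive interference task in pediatric anxiety", so an error contrast is as easy to reach for as an incongruent-versus-congruent one.

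**Connectivity source.** Section 9.1 says "Functional activation and connectivity of these brain regions are assessed using a conflict interference computer task performed during MRI scanning". Section 4.1 describes "MRI scanning during a cognitive interference task and resting-state to assess brain activation and functional connectivity in the TCN".

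**Labels.** Sections 1.1, 3 and 9.1 make the TCN primary and anxiety secondary. Section 4.1 calls change in clinician-rated anxiety the primary outcome variable, and Section 8.2 calls the PARS the primary outcome measure.

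**The concern.** An analyst could follow the plan exactly, examine several regions, contrasts and connectivity measures, find one group-by-time effect at p = 0.004 uncorrected, and report the primary hypothesis as supported. Another could follow it equally exactly, correct within a mask, and report no effect. A reader of the results could not tell from the plan which was intended.

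Two things are at stake. One is the false-positive rate of the headline claim. The other is the study's stated purpose in Section 9.2, which is to supply effect sizes for a larger application. An effect picked out because it passed an uncorrected threshold in a small sample tends to be overstated, and a later sample size built on it would be too small.

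**Working it through.** **The plan's own figures.** Section 9.2 gives no power calculation and no section states an overall error rate, so there is no design figure to reproduce. The only related figure is the expected usable sample in Section 5, 32 and 14. From its retention (96.2%) and motion (89%) rates, 36 × 0.962 × 0.89 = 30.8 and 18 × 0.962 × 0.89 = 15.4. The total is 46.2 against the stated 46, and the split differs by between one and two per arm.

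**Regional tests at 0.005 two-sided.** The number of tests k is assumed, because the plan does not give it.
- k = 2: one activation and one connectivity test.
- k = 6: the three regions of Section 2.2.2 plus their three pairs, with one contrast and task connectivity only.
- k = 12: 3 regions × 2 contrasts + 3 pairs × 2 connectivity sources.
- k = 42: the same with hemispheres separate, 6 × 2 + 15 × 2.

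If independent, the family-wise error is 1 − 0.995^k. In the hypothesised direction only (a larger increase with CBT+CCT) it is 1 − 0.9975^k. Correlated values come from an equicorrelated normal model.

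| k | Independent | Correlation 0.5 | Correlation 0.8 | Hypothesised direction, independent | Hypothesised direction, correlation 0.5 |
|---|---|---|---|---|---|
| 2 | 1.0% | 1.0% | 0.9% | 0.5% | 0.5% |
| 6 | 3.0% | 2.6% | 1.8% | 1.5% | 1.3% |
| 10 | 4.9% | 3.9% | 2.3% | 2.5% | 1.9% |
| 12 | 5.8% | 4.5% | 2.6% | 3.0% | 2.2% |
| 42 | 19.0% | 10.8% | 4.7% | 10.0% | 5.4% |

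The break-even is 0.05/0.005 = 10 tests by Bonferroni.

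**Voxelwise testing.** Section 8.1.3 gives 2.4-mm voxels (2.4³ = 13.8 mm³). Assumed: that voxel size is kept in analysis; cubic masks of 729, 3,375 and 6,859 voxels (10.1, 46.7 and 94.8 mL); smoothness of 6, 8 and 12 mm FWHM; no extent threshold, since none is stated; and a Gaussian field standing in for the t field. The expected number of false-positive voxels is 0.005 × V = 3.6, 16.9 and 34.3, whatever the correlation. The chance of at least one at |z| > 2.807, from 3,000 simulated null fields per cell:

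| Mask | 6 mm | 8 mm | 12 mm |
|---|---|---|---|
| 10 mL | 72% | 53% | 27% |
| 47 mL | 99.8% | 96% | 69% |
| 95 mL | 100% | 99.7% | 90% |

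In the hypothesised direction the range is about 14% to over 99%. By symmetry a directional rate cannot be below half the two-sided rate (27.4%/2 = 13.7%), and a check with 1,000 fields per cell gave 14% to 99.8%.

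**Activation and connectivity together.** If each is properly corrected at 0.05 and either counts as success, the error is 1 − 0.95² = 9.75%, or 9.1% and 7.8% at correlation 0.5 and 0.8.

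**Precision for planning.** The 95% half-width for a standardised difference d in change, at 32 versus 14, is 1.96 × √(1/32 + 1/14 + d²/92) = 0.631 at d = 0.3 and 0.636 at d = 0.5. With a 31 and 15 split it is about 0.62.

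**The case against.** The strongest reply is that Section 9.3.2 can be read as a few network- or region-level ANOVAs on the interference task that Section 9.1 names. On that reading there are about 2 to 6 tests, and 0.005 uncorrected is stricter than a 5% family-wise rate. The larger regional counts need an error contrast taken from the background and a resting-state source taken from the design overview. The claim is also directional, and only about half of the two-sided regional errors would support it. All of this stands, so a reader who infers that the plan simply fails to control its false-positive rate goes further than the text allows. But the plan does not commit to the benign reading either, and a voxelwise analysis at 0.005 would comply with it.

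The 0.005 might be meant as a cluster-forming threshold. No cluster or extent rule appears, so the text does not support that.

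The study is a non-randomised pilot (Section 6.3) with no power claim. That lowers the stakes, but Sections 9.3.1 to 9.3.3 still plan significance tests.

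Two stronger readings of the label conflict are tempting. One is that the plan has two competing confirmatory primaries. The Section 4.1 sentence leads directly into regressions and probably names their dependent variable, as in Section 9.3.5, and the Section 8.2 phrase sits in a deviation rule. Neither sets up a second confirmatory test. The other is that missed scans escape deviation reporting while missed PARS ratings do not. Section 8.2 does not mention missed scans, and Sections 1.3, 4.1, 4.4 and 8.1.3 give the investigator discretion over scans or over completion of study activities, so this is only an inference.

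**Conclusion.** The point holds in a conditional form. Section 9.3.1 permits an uncorrected primary result, gives no rule for when correction governs, and leaves mask, contrast, level of testing and number of tests open. Error control of the primary claim is therefore undetermined by the plan, rather than shown to be lost.

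Up to 10 fixed regional tests there is no inflation. At 42 tests the rate is 19% if independent and 11% at correlation 0.5 (about 10% and 5% in the hypothesised direction). Voxelwise without an extent threshold it is roughly 27% to 100% two-sided. The test counts, correlations, mask volumes and shape, smoothness and voxelwise testing itself are assumptions, so these figures show how much the open choice matters and do not estimate this trial's error rate. The 9.75% figure applies only if activation and connectivity are corrected separately and either suffices.

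This should be fixed, but it does not invalidate a pilot. The label conflict is a minor wording matter.

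**What to change.** 1. In Section 9.3.1, remove the uncorrected threshold for the primary group-by-time test and label any uncorrected imaging result exploratory.
2. Before any group comparison of imaging data, fix one TCN mask, one MSIT contrast, and one connectivity metric with one data source, and make Sections 4.1 and 9.1 agree. The content is the sponsor's choice.
3. State the test: either the mask mean at two-sided 0.05, or voxels at 0.05 corrected within the mask by one named method. A mask mean at 0.05 is looser per test than 0.005, but as a single pre-fixed test it holds its level. FWE or FDR is a matter for the sponsor, provided one is named.
4. State how error is shared between activation and connectivity. Holm is one option (smaller p against 0.025); making connectivity secondary is another.
5. Report the pre-fixed mask-mean effect size with its 95% confidence interval whether or not it is significant. A half-width of about 0.63 to 0.64 SD at 32 versus 14 tells the next trial's planners how little is known.
6. Separately, reconcile the primary labels for anxiety and PARS in Sections 4.1 and 8.2 with Sections 1, 3 and 9. The deviation rule can keep PARS by name, and it would help to say how missed scans are handled.

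Cost: wording only, with no new data or visits. A mask mean may dilute a focal effect, and some regional findings would be reported as exploratory.
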